2. LIST OF ABBREVIATIONS

Term	Definition / description
AD	Atopic dermatitis
ADA	Anti-drug antibodies
ADS	Analysis dataset
AE	Adverse event
AESI	Adverse event of special interest
ALT	Alanine aminotransferase
ALQ	Above limit of quantification
AST	Aspartate aminotransferase
ATC3	Anatomical-Therapeutic-Chemical classification level 3
BI	Boehringer Ingelheim
BIcMQ	Boehringer Ingelheim-customised MedDRA query
BLQ	Below the lower limit of quantification
BM-SAP	Biomarker Statistical Analysis Plan
BMI	Body mass index
BSA	Body surface area
CARE	Clinical data analysis and reporting environment
CI	Confidence interval
CMH	Cochran-Mantel-Haenszel
CRP	C-reactive protein
CTP	Clinical trial protocol
CTR	Clinical trial report
CV	Arithmetic coefficient of variation
DBLM	Database lock meeting
DILI	Drug Induced Liver Injury
DLQI	Dermatology Life Quality Index
DMC	Data Monitoring Committee
ECG	Electrocardiogram
eCRF	Electronic case report form
eDISH	Evaluation of drug-induced serious hepatotoxicity
EASI	Eczema Area and Severity Index
EMA	European Medicines Agency

Term	Definition / description
EoS	End of study
ES	Enrolled set
EX	Exclusion
FAS	Full analysis set
FAS-C	Full analysis set including completers
gCV	Geometric coefficient of variation
gMean	Geometric mean
HIV	Human immunodeficiency virus
HLT	High level term
HLGT	High level group term
IC	Informed consent
ICH	International Council for Harmonisation of Technical Requirements for Pharmaceuticals for Human Use
IGA	Investigator Global Assessment
IgE	Immunoglobulin E
IN	Inclusion
iPD	Important protocol deviation
IQR	Interquartile range
IQRMP	Integrated Quality and Risk Management Plan
IRT	Interactive response technology
LD	Last dose
LLOQ	Lower limit of quantification
Max	Maximum
MedDRA	Medical Dictionary for Regulatory Activities
Min	Minimum
MMRM	Mixed Model Repeated Measures
MQRM	Medical quality review meeting
N	Number of observations
NA	Not applicable
NR	Non-Responder
OL	Open label
PD	Pharmacodynamic(s)
PE	Primary endpoint

Term	Definition / description
PK	Pharmacokinetic(s)
PKS	Pharmacokinetic parameter set
PPS	Per protocol set
Q1	1 st quartile
Q3	3 rd quartile
R	Responder
RAGe	Report appendix generator
RCTC	Rheumatology common toxicity criteria
REML	Restricted maximum likelihood
RPM	Report planning meeting
RS	Randomized set
SAE	Serious adverse event
SAF	Safety analysis set
SAF-OL	Safety analysis set in the open-label treatment period
SAP	Statistical analysis plan
SCORAD	SCORing of Atopic Dermatitis
SD	Standard deviation
SDL	Subject data listing
SI	Système international d'unités
SMQ	Standardised MedDRA query
SOC	System Organ Class
TB	Tuberculosis
TSAP	Trial statistical analysis plan
UDAEC	User-defined AE concepts
ULN	Upper limit of normal range
ULOQ	Upper limit of quantification
VAS	Visual analogue scale

3. INTRODUCTION

As per ICH E9 (1), the purpose of this document is to provide a more technical and detailed elaboration of the principal features of the analyses described in the CTP and its amendments, and to include detailed procedures for executing the statistical analysis of the primary and secondary variables and other data.

This trial statistical analysis plan (TSAP) assumes familiarity with the CTP. In particular, the TSAP is based on the planned analysis specification as written in CTP Section 7 “Statistical Methods and Determination of Sample Size”. Therefore, TSAP readers may consult the CTP for more background information on the study, e.g., on study objectives, study design and population, treatments, definition of measurements and variables, planning of sample size, randomisation.

Pharmacokinetic (PK) parameters will be calculated using WinNonlinTM software (version 6.3, Certara USA Inc., Princeton, NJ, USA).

The statistical analyses will be performed within the validated working environment CARE, including SAS™ (current Version 9.4, by SAS Institute Inc., Cary, NC, USA), and a number of SAS™-based tools (e.g., macros for the analyses of AE data or laboratory data; Report Appendix Generator system (RAGe) for compilation/formatting of the CTR appendices).

This TSAP will document the features of the primary week 16 analysis (to be performed once all randomized patients have completed through the week 16 visit), as well as the final trial analysis including data beyond week 16 (to be performed once all patients have completed the trial). A separate Interim Statistical Analysis Plan describes the analyses that were performed once 75% of patients had completed at least 4 weeks of treatment.

4. CHANGES IN THE PLANNED ANALYSIS OF THE STUDY

NA

5. ENDPOINTS

For all endpoints and unless explicitly specified otherwise, Week numbers refer to specific Visit numbers using extended time windows as defined in [Table 6.7: 1](#) and [Table 6.7:2](#).

For all endpoints and unless explicitly specified otherwise, End-of-Study visit refers to V10 (Week 28) for Responders and V11 (Week 44) for Non-Responders, using extended time windows as defined in [Table 6.7: 1](#) and [Table 6.7:2](#).

Responders are defined as patients who attain at least 75% reduction in Eczema Area and Severity Index (EASI) score compared to baseline at Week 16. Non-Responders are defined as patients who do not achieve at least 75% improvement from baseline in EASI score at Week 16.

For handling of missing data and corresponding sensitivity analyses, see [Section 6.6](#).

Definition of baseline is provided in [Section 6.7](#).

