4.1.3 Method of assigning patients to treatment groups

An Interactive Response Technology (IRT) will be used to screen and randomise eligible patients, perform subsequent drug assignment, manage initial/re-supply ordering of drug supplies and handle emergency un-blinding. The investigator will receive all necessary instructions to access IRT from the Sponsor or chosen provider. Detailed IRT functions and procedures will be documented in the user requirement specifications mutually agreed to by the sponsor and the IRT vendor. Patients will be randomly assigned to one of the treatment groups through the assignment of medication which will be treatment group-specific (Section [3.1](#)). For technical and statistical features of the treatment allocation process, please see Sections [4.1.4](#) and [7.6](#).

During Visit 2 (W0) and after the patient's eligibility has been confirmed, the treatment will be assigned via IRT. Patients will be randomized to receive BI 655130 600 mg or placebo in a ratio of 2:1. The assignment will occur in a blinded fashion via IRT.

During Visit 7 (W16) patients will be evaluated with the EASI scoring system (see Section [5.1](#)) and based on the response will be reassigned via IRT to receive BI 655130 600 mg or no treatment at all. The re-assignment will occur in an open label fashion.

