6.2.2.2 Unscheduled visits

During the treatment period patients may be seen at an unscheduled visit if they experience worsening of the disease or have AEs that in the opinion of the investigator need intervention (e.g. escape or rescue treatment) or repeated laboratory testing.

The unscheduled visit may include additional collection of blood samples for safety reasons. The unscheduled visit may also include additional assessments deemed necessary by the investigator such as laboratory samples, ECGs, or other procedures that were missed at a previous visit. All unscheduled visits (including the reason for the visit) should be described and documented in the medical/source record, and in the eCRF.

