V1	Screening	- 28 to -7	n/a			$-\infty$	0
V2	Day 1	Day 1	n/a	1 ^A	1	1 ^A	1
V3	Week 2	Day 15	+/- 3	12	18	2	21
V4	Week 4	Day 29	+/- 3	26	32	22	42
V5	Week 8	Day 57	+/- 3	54	60	43	70
V6	Week 12	Day 85	+/- 3	82	88	71	98
V7	Week 16	Day 113	+/- 3	110	116	99	Week 16 visit date

Days are counted relative to the day of first treatment, which is defined as Day 1.

^A Note that measurements made at Day 1 and assigned to the on-treatment period (because mistakenly made after start of infusion of trial treatment) via assessment on date and time (i.e. safety laboratory) will not be assigned to Day 1. Such data will be listed only.

[Table 6.7:1](#) needs to be taken only when the measurement occurs between randomisation date and primary endpoint visit date (Week 16 visit date). Any unscheduled visits after Week 16 visit date will not be taken into account in [Table 6.7:1](#).

For measurements after the primary endpoint visit date (Week 16 visit date), including unscheduled visits, refer to the [Table 6.7:2](#).

Table 6.7: 2 Time windows for assignment of efficacy, safety lab, vital signs, and biomarker measurements to visits for statistical analysis after Week 16 visit date

Visit number/ name	Visit label	Planned day	Time window (Days)				
			Window (per CTP)	Start (per CTP)	End (per CTP)	Start (extended)	End (extended)
V7.1*	Week 16OL					Week 16 visit date+1	126
V8	Week 20	Day 141	+/- 3	138	144	127	154
V9	Week 24	Day 169	+/- 3	166	172	155	182
V10**	EoS for R	Day 197	+/- 3	194	200	183	210/
						LD+16 weeks/EoS visit date	
V11a***	EoS for NR	Day 228	+/- 3	225	231	211	238/
						LD+16 weeks /EoS visit date	
V11b***	EoS for NR	Day 309	+/- 3	306	312	239	LD+16 weeks /EoS visit date

Days are counted relative to the day of first treatment, which is defined as Day 1.

LD = Last dose of treatment

EoS = End of Study

R = Responder

NR = Non-Responder

* For vital signs, measurements after EASI responder-non-responder assessment are assigned to Week 16 (V7), after first open-label (OL) treatment

** V10 EoS applies to patients who responded at Week 16 (up to LD+16 weeks); Non-responders receive the last dose of the BI655130 at that Week 28 visit (up to day 252)

*** V11a and V11b apply to patients who did not respond at Week 16 and were re-allocated to BI655130 treatment

Repeated and unscheduled efficacy, safety and biomarker measurements will be handled similarly to scheduled measurements and will also be assigned to a time window depending upon the date of measurement.

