Only one observation per time window will be selected for statistical analysis at a particular visit – the value which is closest to the protocol planned visit day will be selected. If there are two observations which have the same difference in days to the planned day, the later value will be selected. If there are two observations on the same day, the worst value will be selected.

Assignment of efficacy observations to visits based on time windows will be based on the non-imputed (observed) data.

For visits without an assigned value based on time windows, a value will thereafter be imputed as defined in [Section 6.6](#). Imputation of efficacy endpoints, when applicable, will be performed based on all available observations obtained during the on-treatment period, irrespective of whether the observation was selected in any time window.

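### The SAP windows give the scheduled visit no priority, so an unscheduled EASI can displace V4, or a V7 held after Day 113, as the analysed value

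*SAP*

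**What the plan says.** SAP section 5 states that for all endpoints "Week numbers refer to specific Visit numbers using extended time windows as defined in" Tables 6.7:1 and 6.7:2. The same section defines Responders and Non-Responders by EASI75 at Week 16, so that status also follows the window-selected value.

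SAP 6.7 gives the selection rules:

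- On unscheduled values: "Repeated and unscheduled efficacy, safety and biomarker measurements will be handled similarly to scheduled measurements".
- One observation per window is kept: "the value which is closest to the protocol planned visit day will be selected".
- Ties: "If there are two observations which have the same difference in days to the planned day, the later value will be selected".
- Same day: "If there are two observations on the same day, the worst value will be selected".

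The Week 16 row of Table 6.7:1 reads "V7 Week 16 Day 113 +/- 3 110 116 99 Week 16 visit date", so the extended window runs from Day 99 to the Week 16 visit date. The text below the table leaves later unscheduled visits out of it. The Week 4 row has planned Day 29, a protocol window of Days 26 to 32 and an extended window of Days 22 to 42. It has no cut-off at V4.

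On conduct, Protocol 6.2.2.2 says that "patients may be seen at an unscheduled visit if they experience worsening of the disease", with further assessments left to the investigator. Protocol 4.1.3 says "During Visit 7 (W16) patients will be evaluated with the EASI scoring system" and bases re-allocation on that response.

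**The concern.** A visit made because the disease is worse is not a neutral sample of the patient's course. If its EASI competes on equal terms with the scheduled one, the analysed value depends partly on the outcome. The arm that flares more has more chances of having a scheduled value replaced by a worse one. With 15 placebo patients planned, single values carry weight.

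The second issue is consistency. Treatment after Week 16 is decided by the EASI at V7. If the SAP analyses a different EASI as Week 16, the reported EASI75 and Responder status can disagree with the status that determined what the patient received.

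**Working it through.** **Inputs.** Windows, planned days, and tie and same-day rules: SAP 6.7. SD 30, difference 25, two-sided alpha 10%, power 80%: Protocol 7.7. Planned arms 30 and 15: protocol synopsis. I take the Week 16 visit date to be the V7 date.

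**Planning figure.** With 2:1 allocation, placebo n = (1.645 + 0.842)² × 30² × (1 + 1/2) / 25² = 6.185 × 900 × 1.5 / 625 = 13.4, rounded up to 14. The total is 3 × 14 = 42, as the protocol states. The sample size is not in question here.

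**Displacement rule.** Let P be the planned day, s the scheduled visit's day and u the day of an unscheduled EASI. Then u displaces s if |u − P| < |s − P|, or if the distances are equal and u is later. At Week 16, u must also not be after s.

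**Week 16 (P = 113).** If V7 is on Day 113 + d with d > 0, the displacing days are 113 − d + 1 to 113 + d − 1, which is 2d − 1 days. Day 113 − d ties, and V7 wins as the later value. If V7 is on or before Day 113, every earlier day is further from Day 113, so none displaces it.

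| V7 on Day | Displaced by an EASI on Days |
|---|---|
| 110 to 113 | none |
| 114 | 113 |
| 115 | 112 to 114 |
| 116 | 111 to 115 |
| 120 (outside the protocol window) | 107 to 119 |

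Separately, a second EASI on the V7 date replaces the V7 value if it is worse, whatever the day.

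**Week 4 (P = 29, both sides open).**

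| V4 on Day | Displaced by an EASI on Days |
|---|---|
| 26 | 27 to 32 (Day 32 ties and is later) |
| 27 | 28 to 31 |
| 28 | 29 to 30 |
| 29 | none |
| 30 | 29 |
| 31 | 28 to 30 |
| 32 | 27 to 31 |

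Weeks 2, 8 and 12 follow the same rules without the V7 cap, and those visits also enter the primary MMRM.

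**Classification.** Table 6.1:2 has only two response and treatment pairings within each randomised arm: Responder with no treatment, and Non-Responder with BI 655130. A patient with EASI75 at V7 gets no further treatment. If a worse EASI is selected as Week 16 and misses EASI75, the SAP calls that patient a Non-Responder on no treatment, and no row applies. SAP 5 would also place End of Study at V11, although a patient re-allocated as a responder ends at V10.

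**Illustrative size.** SE = 30 × √(1/30 + 1/15) = 9.49. One placebo value 30 points worse moves the placebo mean by 30/15 = 2.0 points, and 2.0/9.49 = 0.21 SE. The same change in one active patient moves the difference by 30/30 = 1.0 point the other way. These are simple means; the MMRM would give slightly different figures.

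**Frequency, by assumption only.** Suppose V7 is spread evenly over Days 110 to 116 and unscheduled EASIs occur at a constant rate of one per patient per 112 days. The mean number of displacing days is (0 + 0 + 0 + 0 + 1 + 3 + 5)/7 = 1.29, and 1.29/112 = 1.1% of patients. At half or double that rate it is 0.6% or 2.3%. For Week 4 the mean is (6 + 4 + 2 + 0 + 1 + 3 + 5)/7 = 3.0 days, or 2.7% (range 1.3% to 5.4%).

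**The case against.** The strongest reply is that the rule is pre-specified, blind to arm and tied to the planned day, and that the cap on the V7 date already protects the primary endpoint. Much of this stands. On four of the seven permitted V7 days, only a worse same-date EASI can displace V7. On the other three, the displacing EASI must fall one to five days earlier. Neither the Flow Chart nor Protocol 6.2.2.2 requires an EASI at unscheduled visits, and SAP section 7 calls all efficacy analyses exploratory.

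It can also be said that V7 is not the cleaner value: Protocol 4.2.1 permits standard of care on worsening, so a V7 shortly after a flare may reflect that treatment. That is a question of how escape treatment is handled. It does not justify letting visit timing choose the value, when the protocol makes V7 the Week 16 evaluation.

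A reader might infer more than the documents support:

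- That a flare visit after V7 can replace it. The cap rules this out.
- That the post-Week 16 efficacy groups are corrupted. SAP 6.1 defines them by the open-label treatment received, and SAP 6.3 defines SAF-OL by medication received after re-allocation.
- That a correct assignment would be flagged as deviation F2.03. That code refers to EASI at V7 and is checked against the IRT entries.
- That the conclusion could flip. A shift of 0.21 SE takes p from 0.10 to 0.065, but only with a chosen starting p, one placebo patient and a gap of a full planning SD between assessments a few days apart. It is not an expected effect.

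**Conclusion.** The point holds in limited form. No SAP rule gives the scheduled visit priority, so a worsening-triggered EASI can become the analysed value. Week 4 is exposed on both sides of the planned day. Week 16 is exposed only when V7 falls after Day 113 or when a worse EASI is recorded on the V7 date. The practical consequences are an outcome-dependent choice of value and, at Week 16, a possible conflict with the re-allocation status that leaves a patient outside Table 6.1:2 and with the wrong End of Study visit.

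The frequency is probably low and cannot be estimated from the documents; the percentages above rest on assumed visit rates and an even spread of visit days. The 2.0-point shift illustrates the weight of one placebo value. The direction of any bias depends on which arm has more such visits, and with equal rates and equal gaps in both arms the expected shift is zero. This is a cheap improvement, not a threat to the trial's conclusion.

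**What to change.** In SAP 6.7, add: *For efficacy endpoints, the value from the scheduled visit is used whenever it lies in the window, including when another value is recorded on the same day. The nearest-day, tie and same-day rules apply only if the scheduled value is missing.*

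In SAP 5 and Table 6.1:2, define Week 16 responder status as the EASI75 result from the V7 assessment used for re-allocation.

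The cost is a sentence in each place and a change of sort order in the programming, with no new data. The downside is that the analysed value will occasionally lie slightly further from the planned day. The change should be fixed before unblinding for the Week 16 analysis.

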18- For Responders (R) the EoS visit must be completed 16 weeks after last treatment, which is at the latest at Week 28 (V10). Responders (R) may complete EOS at any point after V7 (Week 16) if the patient drops to an EASI 50 score prior to the planned EOS. For Non Responder (NR) patients who have achieved EASI 50 and plan to participate in the extension trial, the EoS visit will be completed no earlier than Week 32. Non Responder patients not participating in the extension trial will complete a V11/FU1 visit between Week 32-44. If a patient should discontinue treatment prematurely every effort should be made to keep the patient in the trial and complete all of the remaining study visits or at a minimum an early EoS visit 16 weeks after last treatment.

[figure not shown]
19- At V1 (Screening) BSA will be assessed for eligibility. From V2 (baseline) onward BSA will be completed as part of SCORAD assessment.

20- Only Non-Responders not participating in the open label extension trial must complete an End of Study Safety Phone Call. V11 and End of Study Safety Phone call can occur on the same day only if the Residual Effect Period (16 weeks after last trial drug infusion) has been reached (WK44). The phone call cannot be performed before the V11.

21- Patients will be asked about their pregnancy status at the End of Study Safety Phone Call.

22- For Non-Responders participating in the open label extension trial, End of Study completion IRT call is registered at V11 as the End of Study Safety Phone Call is not required. For Non-Responders not participating in the open label extension trial, End of Study completion IRT call is registered only at End of Study Safety Phone Call (WK44). V11 is not registered in IRT.

TABLE OF CONTENTS

TITLE PAGE	1
CLINICAL TRIAL PROTOCOL SYNOPSIS	2
FLOW CHART	6
TABLE OF CONTENTS	10
ABBREVIATIONS	13
1. INTRODUCTION.....	16
1.1 MEDICAL BACKGROUND	16
1.2 DRUG PROFILE	17
1.2.1 Mode of Action	17
1.2.2 Nonclinical pharmacology.....	17
1.2.3 Clinical experience	18
1.3 RATIONALE FOR PERFORMING THE TRIAL	20
1.4 BENEFIT - RISK ASSESSMENT.....	20
2. TRIAL OBJECTIVES AND ENDPOINTS.....	22
2.1 MAIN OBJECTIVES, PRIMARY AND SECONDARY ENDPOINTS.....	22
2.1.1 Main objectives.....	22
2.1.2 Primary endpoint	22
2.1.3 Secondary endpoint(s)	22
	
3. DESCRIPTION OF DESIGN AND TRIAL POPULATION	24
3.1 OVERALL TRIAL DESIGN AND PLAN	24
3.2 DISCUSSION OF TRIAL DESIGN, INCLUDING THE CHOICE OF CONTROL GROUP(S)	25
3.3 SELECTION OF TRIAL POPULATION	25

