6. GENERAL ANALYSIS DEFINITIONS

6.1 TREATMENTS

For basic study information on the treatment to be administered, assignment to treatment, and selection of dose, cf. Section 4 of the CTP.

In the blinded treatment phase, all patients will receive either intravenous doses of 600mg of BI 655130 solution for infusion (at weeks 0, 4, 8, and 12), or Placebo.

At Week 16, all patients will be evaluated with the EASI Score. Non-responders (EASI < 75) will be re-allocated to receive BI open label trial drug from Week 16 through Week 28; they will be followed until Week 44. Responders (EASI >= 75) will be re-assigned to receive no further trial treatment but will be expected to come to all visits up to Week 28, when EOS visit is planned.

The following trial periods/phases are defined:

Table 6.1: Flow chart of trial period/phases

Trial phase	Description	Start (included)	End (excluded)
Screening phase	Screening	Date of informed consent	Date of start of first infusion of study drug (day 1).
Blinded Treatment phase	Randomised On-treatment period	Date of start of infusion of first study drug (Day 1)	Week 16 visit date + 1 day
Open label Treatment phase ¹	Re-allocation period (Either open label BI655130 or No treatment)	Week 16 visit date + 1 day	Date of EoS Participation visit + 1 day

Dates are defined individually per patient. If more than one date is associated with a specific visit, measurements associated with a specific date are assigned to a study analysis phase according to the rules specified in the table. An analysis phase will not extend beyond the start date of the following phase.

¹ Non-responders (i.e. EASI<75) at Week 16 will be re-allocated to BI655130 600mg IV open label and will continue in the trial until Week 44. Responders (EASI>=75) at Week 16 will be re-allocated to no treatment and will be observed until Week 28 or the day when they return to a 50% reduction in EASI score (EASI50) and start the treatment in the extension trial.

Patients who discontinue the treatment but will continue on trial visits will be included in analyses with the available data. For patients who discontinue trial prematurely only available data will be used in the analyses.

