7.8.1 Adverse events

AEs will be coded with the most recent version of MedDRA.

The analyses of AEs will be descriptive in nature. All analyses of AEs will be based on the number of patients with AEs and not on the number of AEs. System organ classes (if applicable) will be sorted according to the standard sort order specified by the EMA, preferred terms (if applicable) will be sorted by total frequency (within system organ class) across all treatment arms.

The analyses of AEs will be performed for double-blind period and for the re-allocation period separately.

For further details on summarization of AE data, please refer to “Analysis and Presentation of Adverse Event data from Clinical Trials” [BI-KMED-BDS-HTG-0066] (7) and “Handling of missing and incomplete AE dates” [BI-KMED-BDS-HTG-0035] (4).

The analysis of AEs will be based on the concept of treatment emergent AEs. If only the start date of an AE is collected (without start time), any AE occurrence on the same day as the first BI 655130 administration will be assigned to the on-treatment phase.

An overall summary of AEs will be presented by treatment.

This overall summary will include summary statistics for the class of other significant AEs (sponsor definition based on ICH E3 (9)) and for the class of AESIs.

The following is considered an AESI in this trial:

- Hepatic injury
- Infusion reactions including anaphylactic reaction
- Severe infections
- Opportunistic and mycobacterium tuberculosis infections

The investigator has to classify on the eCRF whether an observed AE was an AESI or not. Only those AEs that are indicated by the investigator as AESI in the eCRF will be analysed in this category.

Based on the specification provided in ICH E3 (9), the sponsor has defined AEs which are to be classified as ‘other significant’. These will include those non-serious AEs which were reported with ‘action taken = Drug withdrawn’ or ‘action taken = Dose reduced’.

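### Non-responders' follow-up after the last infusion depends on EASI50 and extension entry; the SAP is inconsistent about this and has no rule for unequal follow-up in open-label AE and late efficacy tables

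*SAP*

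**What the plan says.** **Protocol.** Non-responders at Week 16 receive their last infusion at V10, Week 28 (Flow Chart footnote 2). What follows depends on the patient:

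- Footnote 18 covers "Non Responder (NR) patients who have achieved EASI 50" who also "plan to participate in the extension trial, the EoS visit will be completed no earlier than Week 32".
- For the rest, the same footnote says: "Non Responder patients not participating in the extension trial will complete a V11/FU1 visit between Week 32-44".
- Footnote 20 adds: "Only Non-Responders not participating in the open label extension trial must complete an End of Study Safety Phone Call". That call is at Week 44. By footnote 22, extension entrants do not need it.

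Section 7.3.4 counts AEs as on-treatment up to 16 weeks after the last dose.

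**SAP.** Section 5 says "End-of-Study visit refers to V10 (Week 28) for Responders and V11 (Week 44) for Non-Responders", subject to the extended windows in the section 6.7 tables. Section 6.1 says of non-responders that "they will be followed until Week 44". Section 7 describes the final analysis as covering a full 44 weeks. However, Table 6.1:1 ends the open-label phase at the patient's own end-of-study date. Table 6.7:2 has two non-responder end-of-study rows, V11a (planned Day 228) and V11b (planned Day 309). The history table says the V11 windows were updated for the protocol amendment.

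On the AE measure, section 7.8.1 states: "All analyses of AEs will be based on the number of patients with AEs and not on the number of AEs". Section 7 takes percentages over all patients in the set. Table 6.1:2 assigns every AE of a non-responder from the Week 16 visit onward to the open-label group, with no stated upper limit. Section 6.6.2 imputes a missing binary outcome as non-response unless both neighbouring visits are successes.

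**The concern.** Length of observation in the open-label period is partly a result of treatment. A patient who does well on open-label drug and moves to the extension is watched for less time than one who does not. A crude percentage of patients with an AE then depends on extension uptake as well as on risk. Section 6.1 plans a whole-trial safety display with this column beside the two randomised columns, and those have unequal follow-up of their own. Safety is part of the primary objective, and the number of patients with drug-related AEs is a secondary endpoint, so these percentages will be read.

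For late efficacy, entrants who finish near Week 32 have no value in the V11b window. A V11b summary may then describe only patients who did not enter the extension. If the non-response imputation is applied there, a patient who left after reaching EASI50 could be counted as an EASI50 failure.

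**Working it through.** **1. The SAP's Week 44.** Week w is Day 7w + 1, so Week 28 is Day 197. Adding the 16-week residual-effect period gives 197 + 112 = 309, which is Week 44. The figure reproduces as the end of that period, but the protocol requires follow-up to that point only of non-responders not entering the extension. (By the same count Week 32 is Day 225; both documents print Day 228.)

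**2. Open-label follow-up by route.**

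| Route | Open-label weeks | Residual-effect weeks observed |
|---|---|---|
| Enters extension, leaves at Week 32 | 32 − 16 = 16 | 32 − 28 = 4 of 16 |
| Does not enter | 44 − 16 = 28 | 44 − 28 = 16 of 16 |

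Week 32 is the earliest exit, so this is the largest imbalance the rule allows for patients who complete as planned. If a share f leaves at Week 32, mean follow-up is 16f + 28(1 − f): 28, 25, 22, 19 and 16 weeks for f = 0, 25, 50, 75 and 100%.

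**3. Effect on the crude AE percentage.** Assume a constant hazard, the same for leavers and stayers. If p is the 28-week risk, the 16-week risk is q = 1 − (1 − p)^(16/28), and the table shows fq + (1 − f)p.

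| p (28 weeks) | q (16 weeks) | f = 25% | f = 50% | f = 75% | Fall at f = 50% |
|---|---|---|---|---|---|
| 20% | 12.0% | 18.0% | 16.0% | 14.0% | 4.0 points |
| 40% | 25.3% | 36.3% | 32.7% | 29.0% | 7.3 points |
| 60% | 40.8% | 55.2% | 50.4% | 45.6% | 9.6 points |

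The hazard does not change along a row, so the fall comes from follow-up alone.

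**4. The randomised columns.** Under Table 6.1:2, non-responders contribute AEs up to the Week 16 visit. Responders contribute up to the earlier of end of study and last randomised dose + 112 days. With that dose at Week 12 (Day 85), this is 85 + 112 = Day 197, about Week 28. Suppose the 16-week risk is 50% at constant hazard, so that the 28-week risk is 1 − 0.5^(28/16) = 70.3%.

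- Randomised column, 20% or 40% responders (assumed): 0.8 × 50 + 0.2 × 70.3 = 54%, or 0.6 × 50 + 0.4 × 70.3 = 58%.
- Open-label column, 70%, 50% or 30% leaving at Week 32: 56%, 60% or 64%.

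Unequal follow-up alone can separate the columns, by an amount that depends on both shares.

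**5. Late efficacy.** As an illustration, take Week 28 EASI improvement as normal with SD 30 (the protocol's Week 16 planning value) and an assumed mean of 30% to 60%. Let patients at 50% or better leave with uptake of 50% to 100%. The mean of those left is then 5.5 to 30.6 points below the mean of all, with no change in any patient. At mean 50% and uptake 50%, a quarter leave and the remaining mean is 42.0%. EASI50 among those left is 0.25/0.75 = 33%, against 50% of all. If leavers are imputed as non-responders it is 0.25/1.00 = 25%.

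**The case against.** A reader might infer that the SAP simply treats every non-responder as followed to Week 44. It does not. Section 5 refers on to the window tables, Table 6.7:2 has an early V11a row, and the open-label phase closes at the individual end-of-study date. That stands. What remains is narrower: text in sections 5, 6.1 and 7 that disagrees with those tables, neither V11 row tied to extension entry, and no rule for unequal follow-up.

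A reader might also infer that the open-label AE column must look worse than a 16-week blinded column, or that efficacy must appear to fade between Week 28 and Week 44. Neither follows. The randomised columns are not 16 weeks for responders. Week 32 is a minimum, so an entrant finishing after Day 238 would fall in V11b. Patients not entering the extension may have V11 at any time in Weeks 32-44, so V11a can hold both groups; their required Week 44 contact is a phone call without an EASI score.

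There are mitigations. AEs are analysed separately for the double-blind and re-allocation periods (section 7.8.1), and a table restricted to the time before Week 16 is planned (section 7.8). Results after Week 16 are descriptive, and no safety hypothesis is tested. Observed-data frequency tables accompany the imputed binary results. Parts of the SAP are redacted, and AE presentation also follows a sponsor guideline not available here. These points limit the consequence. None of the visible text supplies a time-at-risk measure, a split by extension entry, or an exemption from imputation after a planned end of study.

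Finally, ending the open-label AE window 4 weeks after the last dose would conflict with the protocol's 16-week residual-effect period. That is correct, so such a window can only supplement the main tables.

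**Conclusion.** The point holds in limited form. Non-responders' observation after Week 28 depends on their outcome and on extension entry, the SAP is inconsistent about it, and crude open-label AE percentages and V11 summaries will partly reflect who left. With a constant common hazard and half leaving at Week 32, the crude open-label AE percentage is about 4 to 10 points lower than under full follow-up, for 28-week risks of 20% to 60%. The efficacy shifts above are illustrations.

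Extension uptake, EASI50 rate, AE risk and responder share are not in the documents, and leavers may have a different hazard, so neither the size nor the net direction is fixed. The documents do not support a claim that safety will look worse, or efficacy will appear to be lost, by a known amount. The Week 16 primary analysis, the sample size and the Weeks 20-28 efficacy results are not touched by this rule. It is a low-cost improvement to descriptive tables.

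**What to change.** 1. Align SAP sections 5, 6.1 and 7 with Table 6.7:2 and with protocol footnotes 18, 20 and 22: V11 in Weeks 32-44 by route, and the Week 44 call only for non-responders not entering the extension.
2. In SAP 7.8.1, keep the AE tables based on the 16-week residual-effect period and add exposure-adjusted incidence per patient-time for all three whole-trial safety columns. A supplementary table over a common window to about Week 32 is optional.
3. Use Week 28 as the last common efficacy time point for non-responders. Show V11a and V11b by extension entry, and do not present them as a continuation of the trend.
4. State in SAP 6.6.2 that non-response imputation is not applied after a planned end of study.

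The work is SAP wording and programming from dates already collected. The cost is one more set of AE tables.
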